## 2.3 Visit windowing

### 2.3.1 Visits

Visit windowing will be performed for all post-baseline visits collected in the database where the patients have more than one post-baseline visit assessment which will be summarized by visit. The screening and baseline visits will not be remapped. The study day for each visit will be derived (see [Section 2.1.1](#) for definition); this day will be then be used to determine the actual visit based on the visit windows outlined in [Table 2-3](#).

As it is planned to have both end of treatment (EoT) and EoS analyses for certain assessments, respective flags will be created for the assessments of interest. The EoT flag will flag all values which occur up and including EoT while the EoS flag will flag all values collected. If more than one remapped visit occurs at a visit, only one will be selected for summary tables but all visits will be listed. Therefore two additional variables will be created which will indicate which values will be used for analysis purposes for EoT and EoS analyses respectively. If more than one remapped post-baseline value for the respective analyses occurs at a visit, only the value closest to the target study day will be selected (see [Section 2.1.1](#) for definition). If there are two observations which have the same difference in days to the target day or if there are two observations on the same day, the first value will be used.

**Table 2-3 Visit windows (monthly)**

Post-baseline timepoint	Visit timepoint (monthly)	Target Study day	Visit window (study days)
3	Month 1	30	2 to 44
4	Month 2	60	45 to 74
5	Month 3	90	75 to 104
6	Month 4	120	105 to 134
7	Month 5	150	135 to 164
8	Month 6	180	165 to 194
9	Month 7	210	195 to 224
10	Month 8	240	225 to 254
11	Month 9	270	255 to 284
12	Month 10	300	285 to 314
13	Month 11	330	315 to 344
14	Month 12	360	>=345

### 2.3.2 Unscheduled visits

All data collected at unscheduled visits will at a minimum be listed.

All safety and exposure to study treatment data collected at unscheduled visits will be used.

## 2.4 Patient disposition, demographics and other baseline characteristics

Demographics, baseline ocular and non-ocular characteristics will be summarized and listed for the FAS for each randomized treatment arm and overall, unless specified otherwise.

No inferential statistical analysis will be performed on these characteristics.

### 2.4.1 Patient disposition

The number and percentage of patients who are screening failures and the reason for screening failure will be presented for all patients screened.

Patient disposition will be summarized for all patients by treatment arm and overall. The number and percentage of patients who completed the study, who discontinued the study early, and also who prematurely discontinued treatment but remained in the study will be displayed.

For those who discontinued the study early or who discontinued the investigational study treatment prematurely but remained in the study, the primary reason for study or investigational study treatment discontinuation will be summarized.

Study completion and investigational study treatment completion will also be summarized by the visit of study termination/ completion and study treatment discontinuation/ completion, respectively.

The number and percentage of patients attending each visit will also be presented by treatment arm.

Furthermore, disposition will be presented in by-patient listings. A study milestones listing will also be provided containing first patient first visit (FPFV), last patient last visit (LPLV) and the trial duration (the time period between FPFV and LPLV), overall and by site.

### 2.4.2 Protocol deviations

PD severity and impact on analysis populations can be found in the DRP and DHP, these are subject to change however and the final definitions and list of PDs will be documented during the BDRM. The PDs are used in excluding entire patients or particular data within a patient from relevant analysis sets. Criteria defining PDs are outlined in the [Appendix 5.3](#).

All PDs will be summarized through presenting the number and percentage of patients with each deviation by treatment arm and total.

Patients with multiple PDs will only be counted once at each level of summarization.

Additionally all relevant (according to medical review) reportable protocol deviations will be summarized under the following deviation categories used in the DRP and DHP. Currently these are:

- Patient did not satisfy relevant inclusion criteria (I)
- Patient met relevant exclusion criteria (E)
- Patient received the wrong treatment or incorrect dose (S)
- Patient developed withdrawal criteria during the study, but not withdrawn (D)

- Patient took an excluded concomitant medication (M)
- Others (O)

In addition, a listing of PDs will be produced including the date and study day of the deviation occurrence with the accompanying deviation code and severity.

#### 2.4.3 **Background and demographic characteristics**

Demographics and baseline data will be summarized and listed for the FAS by treatment arm and overall, unless specified otherwise. Descriptive statistics will be provided for the below demographics and baseline characteristics:

##### **Demographics**

Continuous variables:

- Age (years)

Categorical variables:

- Age group (<65, >=65 years)
- Sex (Male, Female)
- Race (Caucasian, Black, Asian, Other)

##### **Non-ocular baseline characteristics**

Continuous variables:

- Vital signs (height [cm], weight [kg], pulse [bpm], systolic and diastolic blood pressure [mmHg])
- Body mass index (BMI) (kg/m^2)
- HbA1c (%)
- Serum Lipid Levels (Cholesterol, HDL-Cholesterol, LDL-Cholesterol, Triglycerides) (mg/dL)
- Estimated number of cigarette pack years
- Time since smoking termination (years)
  - Note: Time since smoking termination is only completed for ex-smokers.
- Time since first diagnosis of diabetes (years)

Categorical variables:

- Pregnancy testing for women of child-bearing potential (Negative, Positive)
- Smoking history (Never smoked, Current smoker, Ex-smoker)
- Time since smoking termination group (< 2, 2 to < 10, 10 to < 20, >= 20 years)
  - Note: Time since smoking termination is only completed for ex-smokers.
- Diabetes type (Type I, Type II)

- Time since first diagnosis of diabetes group (< 2, 2 to < 10, 10 to < 15, 15 to < 20, >= 20 years)

### **Ocular baseline characteristics**

Continuous variables:

- Time since first diagnosis of DME (years) (study eye, fellow eye)
- BCVA (letters) (study eye, fellow eye)
- Intraocular pressure (mmHg) (study eye, fellow eye)

[REDACTED]

Categorical variables:

- Time since first diagnosis of DME group (< 2, 2 to < 10, 10 to < 15, 15 to < 20, >= 20 years) (study eye, fellow eye)
- Study eye selection (Left, Right) (study eye)

[REDACTED]

The following assessments presenting retinal characteristics are provided by the CRC.

### **OCT baseline characteristics (from CRC)**

Continuous variables:

- CSRT ( $\mu$ m) (study eye)
- [REDACTED]
- FCP thickness ( $\mu$ m) (study eye)
- [REDACTED]
- [REDACTED]
- [REDACTED]
- [REDACTED]

Categorical variables:

- [REDACTED]
- [REDACTED]
- [REDACTED]
- [REDACTED]
- [REDACTED]
- [REDACTED]

- Automated segmentation of CSRT (Correct, Error manually corrected, Manual correction too time-consuming, Not gradable, NA) (study eye)
- [REDACTED]
- CSRT  $\geq 300 \mu\text{m}$  (Yes, No, Not gradable, NA) (study eye)
- [REDACTED]
- Automated or manually corrected segmentation of CSRT by OCT software (Correct, Manually measured, Not gradable, NA) (study eye)
- [REDACTED]

[figure not shown]
Note: The descriptive statistics summary table and listing for OCT baseline characteristics will also be produced using the unadjusted CSRT and FCP thickness values.

#### **Color Fundus Photography (CFP) baseline characteristics (from CRC)**

The following variables will only be listed by treatment arm.

Categorical variables:

- CFP modality available? (Yes - Required; Yes - Not required; No – Required; No - Not required)
- CFP quality OD (Excellent, Good, Adequate, Poor, NA)
- CFP quality OS (Excellent, Good, Adequate, Poor, NA)
- CFP submission acceptance (Completely acceptable, Acceptable with remarks, Not acceptable, NA)

### **DRS baseline characteristics (from CRC)**

Categorical variables:

- DRS (Mild\*NPDR, Moderate\*NPDR, Severe\*NPDR, Proliferative Diabetic Retinopathy, Status post panretinal laser coagulation - not gradable, NA) (study eye, fellow eye)

### **General image grading characteristics (from CRC)**

Categorical variables:

- Confirmed eligibility of study eye (Yes, No, NA)
- Concerns for fellow eye to be considered as study eye alternatively at screening (Yes, No, NA)
- Adequacy of image quality for eligibility (Yes, No, Questionable, Not gradable, NA)
- Presence of any diabetic macular edema (Yes, No, Questionable, Not gradable, NA) (study eye)
- No presence of concomitant conditions that would prevent improvement (Yes, No, Questionable, Not gradable, NA) (study eye)
- No presence of structural damage in the center of the macula (Yes, No, Questionable, Not gradable, NA) (study eye)
- No presence of vitreous hemorrhage impairing the adequate diagnosis (Yes, No, Questionable, Not gradable, NA) (study eye)
- No presence of relevant vitreofoveal adhesion or epiretinal membrane with foveal involvement (Yes, No, Questionable, Not gradable, NA) (study eye)
- No presence of proliferative vitreoretinopathy (Yes, No, Questionable, Not gradable, NA) (study eye)
- No presence of central retinal neovascularizations (Yes, No, Questionable, Not gradable, NA) (study eye)
- Presence of signs of vitreous hemorrhage (Yes, No, Questionable, Not gradable, NA) (study eye, fellow eye)

- Presence of signs of panretinal laser coagulation (Yes, No, Questionable, Not gradable, NA) (study eye, fellow eye)
- Presence of signs of laser treatment of the macula (Yes, No, Questionable, Not gradable, NA) (study eye, fellow eye)
- Lens status (Phakic, no marked opacity; Phakic, marked opacities; Pseudophakic; Aphakic; Other; Not gradable; NA) (study eye, fellow eye)
- Capillary non-perfusion – general (Yes, No, Questionable, Not gradable, NA) (study eye, fellow eye)
- Capillary non-perfusion – involvement of center (Yes, No, Questionable, Not gradable, NA) (study eye, fellow eye)
- Capillary non-perfusion – area extent ( $\leq 3$  PD,  $> 3$  PD  $\leq 5$  PD,  $> 5$  PD  $\leq 7$  PD,  $> 7$  PD  $\leq 10$  PD,  $> 10$  PD, NA) (study eye, fellow eye)

The following ocular assessments (confocal scanning laser ophthalmoscope [cSLO]) are optional. They will only be performed for patients with the respective additional informed consent in participating centers equipped with the respective device.

#### **cSLO baseline characteristics (from CRC)**

Categorical variables:

- cSLO modality available? (Yes - Required; Yes - Not required; No – Required; No - Not required)
- IR image quality (Excellent, Good, Adequate, Poor, NA)
- Multicolor quality (Excellent, Good, Adequate, Poor, NA)
- FAF quality (Excellent, Good, Adequate, Poor, NA)
- cSLO submission acceptance (Completely acceptable, Acceptable with remarks, Not acceptable; NA)

#### **2.4.4 Medical history**

The number and percentage of patients from the FAS with relevant medical history (ocular and non-ocular) and current medical conditions will be tabulated by system organ class (SOC) and PT of the current Medical Dictionary for Regulatory Activities (MedDRA) dictionary (version 19.1 or higher). The SOCs will be presented in alphabetical order. PTs will be ordered by treatment arm and total by decreasing proportion in the total group.

Separate summaries will be presented for histories and current medical conditions (documented in the database as still active at the start of the study). Additionally, these tables

will be provided separately for ocular (presented for both eyes in addition to study eye and fellow eye separately) and non-ocular histories and conditions.

For handling of missing or incomplete start and end dates, see [Appendix 5.1.3](#) of this document.

Additionally all information will be listed including the investigator reported term and the diagnosis/ surgery date and day.

## 2.5 **Treatments (study treatment, concomitant therapies, compliance)**

Summaries will be presented for the Safety Set. All analyses will be presented for the study eye only, unless specified otherwise.

The fellow eye is not treated with investigational study treatment and will therefore not be applicable for [Section 2.5.1](#).

### 2.5.1 **Study treatment/ compliance**

#### 2.5.1.1 **Investigational treatment**

Descriptive statistics for the total number of ranibizumab injections will be presented for each treatment phase separately and overall by treatment group and total. Summary statistics for the number of injections per patient will be presented by frequency distribution (number of patients with 1 injection, number of patients with 2 injections, on up to the maximum number of injections for any one patient) for the given treatment phase and overall, and cumulatively.

Descriptive statistics will also be provided by treatment arm and total for:

- duration of the overall study period
- duration of the initial treatment phase
- duration of the maintenance phase
- duration of time between visits (overall and for maintenance phase)
- duration of time between injections (overall and for maintenance phase)

This table will also be repeated by actual treatment strategy. Furthermore, duration of time between visits and duration of time between injections will be presented overall and by actual treatment strategy from month 4 onwards

At each visit, the number and percentage of patients receiving or not receiving a ranibizumab injection will be summarized from baseline to month 11. Additionally, the reasons for no study treatment given will be summarized. This will include details for disease activity as recorded in the Ranibizumab dose administration eCRF (no disease activity, disease activity stable with maximum BCVA, BCVA and disease activity stable, Adverse event or disease activity present but patient refused additional study treatment). The denominator at each visit will be the number of patients for which a study treatment decision was recorded in the eCRF at that visit.

A frequency table will be presented at each visit showing the number and percentage of patients for overall and each individual stability compliance assessment category (see [Section 2.1.1](#) for definition of the stability compliance assessment) who stopped treatment due to one of the following three stability criteria:

- No disease activity (BCVA maximum, CRT minimum and no further signs of activity in morphologic parameters)
- Disease activity stable with maximum BCVA (no further improvement of other morphologic parameters)
- BCVA and disease activity stable (no further improvement of BCVA and other morphologic parameters).

By-patient listings for ranibizumab injection administration will be provided.

Descriptive statistics presenting the total number of cases (patient and event counts) where patients were treated not in line with the stability compliance assessment (see [Section 2.1.1](#) for definition of such patients) and the frequency distribution (number of patients treated in line with the stability compliance assessment, number of patients treated once not in line with the stability compliance assessment, number of patients treated twice not in line with the stability compliance assessment, on up to the maximum number of cases where patients were treated not in line with the stability compliance assessment for any one patient) will be presented for the maintenance phase by treatment arm and total. Alignment with the stability compliance assessment (Yes, No) will be included in the ranibizumab injection administration by-patient listing.

Descriptive statistics will be provided for the duration of:

- study observation period (Date of last visit – Date of first administration of study treatment + 1 day)
- study treatment period (Date of last administration of study treatment – Date of first administration of study treatment + 1 day).

The duration will be categorized into periods of 30 days. Descriptive statistics for the duration of study treatment period will also be provided by overall stability compliance assessment (refer to [Section 2.1.1](#) for definition).

The number and percentage of patients for whom the visit interval was increased, kept or reduced will be summarized by visit. Additionally, the reasons for increasing, reducing, or keeping the visit interval the same, as recorded in the Visit Interval eCRF will be listed. This listing will be repeated for those patients with a treatment pattern which includes X (see [Section 2.5.1.1.1](#) for definition), the listing will also include the visit structure and associated visit dates.

The source of confirmation of disease activity as provided in the eCRF (BCVA, OCT, Ophthalmoscopy, CFP, FA, Other) will be also be listed.

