3.2 Rationale of study design

Ranibizumab 0.5mg has been approved in the EU since 2011 for VI due to DME. The current standard of care treatment is PRN treatment with monthly monitoring (Stellungnahme der Deutschen Ophthalmologischen Gesellschaft, der Retinologischen Gesellschaft und des Berufsverbandes der Augenärzte Deutschlands, 2013, Bandello 2012). Ophthalmologists gained experience in treating modalities of DME patient with anti-VEGF therapies based on VA-changes and disease activity in the past years.

In RESTORE study with monthly monitoring and PRN treatment median of injections after 12 months were 7.0 in both ranibizumab groups (Mitchell et al. 2011). But already in the second half of the first year the injection rate decreased to 2.4 and 2.7 in the respective ranibizumab arms (Schmidt-Erfurth et al. 2014). After 24 months 11.0 to 11.3 injections were needed in both ranibizumab arms (Lang et al. 2013) that corresponds to 2.5 and 3.9 injections in the second year. Starting with the second half of the first year, rapidly declining injection frequencies over time did not correspond to lesser monitoring visits. Patients were still seen on a monthly basis. Therefore we suppose that monitoring intervals can be extended at least for some patients.

To address these disparity between injection frequency and monitoring visits, in the RETAIN study a treat and extend (T&E) treatment regimen was evaluated. Primary objective was the visual acuity change 12 and 24 months with two T&E treatment arms (ranibizumab with and without additional laser photocoagulation) tested against a PRN treatment (ranibizumab mono therapy). In this study the T&E arms treatment intervals could be extended by 1 month if patient was stable regarding vision to a maximum interval of 3 months between injections. T&E regimen were non-inferior to PRN treatment after 12 and 24 months (mean average

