change of best corrected visual acuity of 5.9 and 6.1 in T&E arms vs 6.2 in PRN arm; Prunte et al.). After 24 months number of visits could be reduced by 40% in T&E arms vs. PRN arms (12.8 and 12.5 vs. 20.5 visits) but there were more injections in the T&E arm than in the PRN arm (median of 12 in T&E and 10 in PRN arm). Higher injection rate were due to protocol requirements, because T&E patients had to be treated at every visit independent of disease activity and patients had to visit the center at least every 3 months. Given the low rate of retreatment in RESTORE study we suppose that retreatment at every visit when a T&E approach is done, probably is not necessary for every patient.

As a conclusion of both RESTORE and RETAIN study we propose that monitoring visits can be reduced by extending monitoring intervals and injections do not have to take place at every visit. We suggest that the investigator should decide when to see the patient for the next visit and when to treat the patient based on disease activity criteria.

With this study we want to test the hypothesis that treatment and visit algorithm done at the discretion of the investigator (DI) will lead to equal visual gain, when compared with a treatment based on the current standard of care (i.e. PRN treatment with monthly monitoring). After initial monthly treatment until maximal VA and no disease activity or no further change in disease activity in both treatment arms, in the DI arm the following approach for monitoring and treatment will be conducted: monitoring intervals will be determined by the physician and will be based on disease activity, as assessed by visual acuity and/or morphological parameters. Intervals between study visits can be extended up to 3 months. Whenever disease activity is present, patients have to be treated. Monitoring for disease activity may include clinical examination, functional testing or imaging techniques (e.g. optical coherence tomography (OCT) or [REDACTED]). This approach may lead to a reduction of visit frequencies in the DI study arm, where physicians will consider when to see the patient for the next visit based on the individual response of the patient.

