5.5.3.3 Instructions for use of investigational treatment

5.5.3.3.1 Treatment of study eye

Arm 1 (DI): after initial monthly treatment until maximum BCVA and no signs or no further change of disease activity, investigator will treat patients at own discretion. There will be no strict recommendations for retreatment or scheduling of upcoming visits except:

- patients need to be monitored at least every 3 months
- patients have to be retreated if any signs of disease activity occur.
- If relevant* loss of visual acuity is the reason for retreatment, next monitoring visit should be scheduled in 4 weeks.

*Relevant loss is defined as loss of visual acuity with a range outside the daily fluctuation of VA in DME patients. E.g. if 3-4 letters loss since last visit is accompanied by fluid in OCT it is highly likely that no daily fluctuation is present, but a true loss of BCVA. Investigator will decide whether VA-loss is relevant or a daily fluctuation and will document the decision and the reasoning in the source data

Due to flexibility of DI-arm, also treatment schemes like PRN, Treat & Extend or fixed dosing are allowed.

Arm 2 (PRN): investigator will treat patients in a PRN scheme, i.e. after initial monthly therapy until maximum BCVA and no signs or no further improvement of disease activity, patients will be monitored every month and retreated if any signs of disease activity occur.

For both treatment arms the following procedures apply:

Initial monthly therapy for both treatment arms: Beginning at baseline, injections are administered monthly until maximum visual acuity is achieved and no signs or no further improvement of disease activity are present.

Disease activity: both functional and morphologic parameters will be taken into consideration when defining disease activity. That could for example be:

- BCVA: change of BCVA
- OCT: increase of retinal thickness
- /FP/ophthalmoscopy: new signs of DME

If retreatment due to new disease activity is necessary, treatment should be continued until:

- maximum BCVA is achieved again or there is no improvement of BCVA compared to previous visit
- there is no further decrease of retinal thickness compared with previous visit
- there is no further regression and no further perspective of regression of other DME characteristics

The interval between 2 ranibizumab injections should not be shorter than 28 days.

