#### 2.5.1.1.1 Investigational treatment pattern

The pattern of ranibizumab treatment administrations will be summarized for both treatment arms from baseline to month 12. For a given patient, the pattern of ranibizumab treatments will be identified by a series of numbers or letters as defined below:

- T indicates EoT visit (only for patients who discontinue treatment early but stay in the study)
- S indicates EoS visit

- X indicates an extended interval where no visit was required in the maintenance phase for a patient due to DI with an actual treatment strategy of Dynamic PRN or Treat & Extend
- M indicates that the patient missed the visit
- 0 indicates that a patient attended the scheduled visit at which study treatment was not given
- 1 indicates that a patient attended the scheduled visit at which study treatment was given
- F indicates a follow-up visit after EoT without further treatment

For example, if a patient received injections at baseline, months 1 to 5, 8 and 10, attended the visit at months 6 and 7 but was not treated in the study eye, missed month 9, discontinued prior to month 12, the ranibizumab treatment pattern for that patient would be 111111001M1S.

Investigational treatment patterns will be listed for all patients.

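### In the maintenance phase, the by-visit injection percentages in SAP 2.5.1.1 are not comparable between arms, because DI patients on a planned extended interval drop out of the denominator.

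*SAP*

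**What the plan says.** SAP 2.5.1.1 plans a by-visit table in which "the number and percentage of patients receiving or not receiving a ranibizumab injection will be summarized from baseline to month 11", together with the reasons for not treating. Its base is explicit: "The denominator at each visit will be the number of patients for which a study treatment decision was recorded in the eCRF". Protocol section 9 makes descriptive output by treatment arm the default, so the two arms' percentages will be shown side by side.

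The visit schedules differ by design once the initial monthly injections end. For PRN, Protocol 5.5.3.3.1 says "patients will be monitored every month and retreated if any signs of disease activity occur". For DI, the same section only requires that "patients need to be monitored at least every 3 months", and Protocol 3.2 states "Intervals between study visits can be extended up to 3 months".

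The SAP recognises the resulting gaps elsewhere. In the treatment-pattern codes of SAP 2.5.1.1.1, "X indicates an extended interval where no visit was required in the maintenance phase for a patient due to DI", separately from M (visit missed) and 0 (attended, not injected). The definition goes on to limit X to patients whose actual strategy is Dynamic PRN or Treat & Extend. The by-visit table has no row for this state and carries no caution.

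Two rules bear on what *visit* means here. SAP 2.3.1 and Table 2-3 remap post-baseline visits to study-day windows. Protocol section 6 has DI visits filed under the next free eCRF visit, whatever the date.

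**The concern.** One row label has two meanings. In PRN, *percentage injected* is close to a percentage of the arm, because nearly everyone is due each month. In DI it is a percentage of those who came in. A DI patient whose visit was rightly postponed received no injection that month, yet does not count as *not injected*.

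The error runs in one direction and grows with the success of the DI regimen: the more visits it spares, the more intensively treated the DI arm appears. The percentages for reasons for no treatment have the same base, so they also leave out the DI patients stable enough to skip a visit.

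The trial is now to be read descriptively (Protocol 9.7, SAP 2.6.2), so much of the interpretation will come from tables like this one. A reader comparing the two columns could conclude that DI led to more injections when injections per patient were equal.

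**Working it through.** The documents state no by-visit injection percentage, so there is no planned figure to reproduce.

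**Formula.** Let *r* be the true injections per patient-month and *a* the share of patients still on study treatment who have a decision in a given monthly window. The planned table shows injected / decisions = *r* / *a*. For PRN, *a* is about 1 apart from missed visits. For DI, *a* is below 1 whenever some intervals are extended.

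**Rate *r*.** Protocol 3.2 says of RESTORE, which used PRN with monthly visits: "But already in the second half of the first year the injection rate decreased to 2.4 and 2.7 in the respective ranibizumab arms". Over 6 monthly visits, 2.4/6 = 0.40 and 2.7/6 = 0.45. I assume this rate in both arms, so that any difference shown is an artefact.

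**Share *a*.** No DI figure is given, so a range is assumed. One anchor is the visit reduction that Protocol 3.2 cites for the Treat & Extend arms of RETAIN, with 12.8 and 12.5 visits against 20.5: 12.8/20.5 = 0.62 and 12.5/20.5 = 0.61. I use 0.62. Carrying it over to DI is an assumption.

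| Assumed DI share *a* | Factor 1/*a* | DI shown, *r* = 0.40 | DI shown, *r* = 0.45 |
|---|---|---|---|
| 1.0 (no extension) | 1.00 | 40% | 45% |
| 0.9 | 1.11 | 44% | 50% |
| 0.8 | 1.25 | 50% | 56% |
| 0.62 | 1.61 | 65% | 73% |

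PRN shows 40% and 45% throughout. At 0.62 the spurious difference is about 25 to 28 percentage points.

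**In patients.** SAP section 3 gives 135 enrolled, about 67 per arm. With *r* = 0.40, each arm has 0.40 × 67 = about 27 injections in a window. PRN shows 27/67 = 40%. With 0.62 × 67 = about 42 DI patients having a decision, DI shows 27/42 = 64% for the same 27 injections.

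**Mixed intervals.** If half the DI arm stays monthly and half is seen every 2 months, *a* = 0.5 × 1 + 0.5 × 1/2 = 0.75. The table then shows 0.40/0.75 = 53% against 40%.

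**With a whole-arm base.** If patients in a planned gap are counted as not injected, both arms show 40% (or 45%), as they should.

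**The case against.** The strongest reply is that the denominator is declared and answers a legitimate question: of the treatment decisions made, how many were to inject? A patient with no visit due has no recorded reason for not being treated, so absence from the reasons rows is not an error in itself. This stands, and is why the per-decision percentage should be kept, under its own label.

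Other planned output also gives context: injected counts in the same table, attendance at each visit by arm (SAP 2.4.1), time between visits and between injections, and the treatment patterns. A careful reader could recover the whole-arm figure. That limits the harm, but the percentage as planned still invites the wrong comparison.

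Two stronger readings are tempting, and the documents support neither.

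- A reader might infer that the trial's injection comparison is biased. It is not. The secondary endpoint is the number of injections (SAP 2.8.1), and SAP 2.8.2 sends it to the total-injection summaries that open 2.5.1.1. Those summaries, by phase and overall with a frequency distribution, do not use this denominator. The by-visit table is not the main dosing table.
- A reader might infer that DI will look about twice as heavily injected. Figures of 80-90% (0.40/0.5 and 0.45/0.5) need every DI patient to be on 2-month intervals, and 100% needs every one to be injected at every visit. Protocol 5.5.3.3.1 also allows PRN or fixed dosing within DI, and the documents give no DI visit frequency.

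The argument also assumes calendar windows. Run on the DI eCRF visit number, the table would fail differently: DI patients would fill consecutive numbers and run out early, and a given visit number would fall at different times in the two arms. The SAP should say which applies.

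**Conclusion.** The point holds for the maintenance-phase by-visit percentages (injected, not injected, and reasons for no treatment). At equal injections per patient-month, the DI percentage averaged over windows is too high by 1/(share of DI patients with a decision). That direction follows from the text, given the study-day windows of Table 2-3.

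The size is conditional. It is about 1.1 times if a tenth of DI windows are skipped and about 1.6 times at the visit reduction cited from RETAIN. It is nil for DI patients kept on monthly visits and during the initial monthly phase. The percentages shown rest on two assumptions: the RESTORE second-half-year rate in both arms, and the range of attendance shares.

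The by-visit counts, total injections per patient, the secondary endpoint on number of injections and the primary analysis are unaffected. This is a fault of presentation and interpretation in an exploratory analysis, worth correcting because the remedy is specific and cheap.

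**What to change.** In SAP 2.5.1.1, for the by-visit injection table:

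1. Assign visits by the study-day windows of Table 2-3, not by the DI eCRF visit number.
2. Use as denominator all Safety Set patients who have not discontinued study treatment or the study before that window. Define this by discontinuation, because the study treatment period in SAP 2.1.1 ends at the last treatment given and would drop patients who simply needed no further injection.
3. Add a row *no visit due (extended interval)*, counted as not injected, and a row *visit missed*.
4. In SAP 2.5.1.1.1, apply code X to every planned DI gap, not only under Dynamic PRN or Treat & Extend, so that the new rows can be derived.
5. Keep the per-decision percentage, including the reasons for no treatment, as a second column labelled as such.

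Protocol 9.3 sets no by-visit denominator for injections, so a change to SAP wording is enough. The cost is minor extra programming, including the wider X rule, and a slightly larger table.
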